Site blinded EDSS examiners: EDSS examiners must have training in the neurological exam and experience conducting EDSS exams. The blinded EDSS examiner should not be the usual treating neurologist of the subject in order to maintain the blind. The blinded EDSS examiners may have access to PHI for subjects from their site only.

Central Research Pharmacy: Portland VA Research Pharmacy will act as the Central Research Pharmacy for the entire study. They will receive bulk study drug from the product donor and redistribute it to US study site Research Pharmacies who then prepare study drug for individual subjects. The Central Research Pharmacy works with the SCC to maintain the randomization lists for each study site. The Central Research Pharmacy has access to PHI for all study subjects.

Site research pharmacies: The US site research pharmacies will receive study drug from the Central Research Pharmacy and package it for individual subjects according to the randomization schedule. They will also provide medication reconciliation reports. The Canadian site research pharmacy will receive study drug directly from the product donor and then perform the same functions as the US site pharmacies. The site research pharmacies to PHI for subjects from their site only.

Clinical Coordinating Center (CCC): VAPORHCS will serve as the CCC. The CCC will serve as the primary communication hub between study sites, study centers, and monitoring bodies.

Data Coordinating Center (DCC): The DCC and the PM will work closely to set up and maintain the study database, create policies and procedures for the study, monitor data quality and accuracy, and help create DSMB reports. The DCC will receive reports from all study sites regarding adverse events (AE), serious adverse events (SAE), unexpected problems (UP), and protocol deviations (PD) and ensure proper reporting to IRBs per reporting requirements.

Statistical Coordinating Center (SCC): The SCC will conduct all data analyses, assist in DSMB reports, and create all final reports, figures, and statistical analysis sections of manuscripts that result from this study. The SCC will have access to PHI from all subjects.

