If a subject wants to withdraw from the study, the subject will contact the site study staff using the contact information and procedures on the ICF and request withdrawal. If a subject withdraws or is removed from the study for any reason and is unable or unsuitable to continue the study procedures off investigational drug, the reason and date of discontinuation of the investigational drug is recorded. At the time of study discontinuation, every effort will be made to schedule the subject for an early termination visit following the procedures for M24 without the MRI or Fall Count Diary if termination is within 6 months of the baseline visit, and M24 procedures with MRI but without fall count if termination is greater than 6 months of the baseline visit. Subjects withdrawn due to reportable adverse events and subjects with adverse events thought related to the study that are ongoing at the final study visit are followed for 30 days or until resolved, whichever is first, or longer per request of the Medical Monitor.

6.0 **Reporting:** All SAE, UAP, and PD are reported to the IRB within defined timelines.

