6.3 Limited reporting of AE

Not all AE captured at sites are reported to the DCC. The limited set of AE reported to the DCC via the REDCap database is according to guidelines in 6.3a below. Serious AE (SAE) and select UP and PD are reported under expedited guidelines according to IRB and other monitoring entity requirements.

AE Intensity*	AE relate study	d to	AE probably related to study	re	possibly lated to study	AE unrelated to study	
Mild	REDCa	p	AE Log only	AE log only		AE log only	
Moderate	REDCap		REDCap	AE log only		AE log only	
Severe	REDCa	ıp	REDCap	REDCap		REDCap	
SAE	REDCa	р	REDCap	REDCap		REDCap	
UP with risk to subjects or others	REDCa	p	REDCap	AE log only		AE log only	
Severe PD: REDCap		Moderate PD: REDCap		Cap. Mild PD: AE log only		E log only	

6.3a Limited reporting of AE, UP, and PD to the DCC. Bold items require expedited reporting to the DCC via REDCap.

* Increases after Screen in CTCAEv5 grades (ALT, AST), new ACR >300mg/g, and new eGFR<60 are always reported in REDCap regardless of intensity or relationship to study. GI distress related and probably related to study of any intensity is reported in REDCap.

ALT, Alanine Aminotransferase; AST, Aspartate Aminotransferase; ACR, Albumin to creatinine ratio

6.4 Adverse event (AE) definition: Any untoward or undesirable, although not necessarily unexpected, event experienced by a human subject that may be a result of:

- The interventions and interactions used in the research.
- The collection of identifiable private information in the research.
- An underlying disease, disorder, or condition of the subject.
- Other circumstances unrelated to the research or any underlying disease, disorder, or condition of the subject.

6.5 Serious Adverse Event (SAE) definition: Any AE that:

- Is fatal.
- Is life-threatening.
- Is persistent or significantly disabling or incapacitating.
- Results in inpatient hospitalization or prolongation of hospitalization.
- Results in psychological or emotional harm requiring treatment.
- Creates a persistent or significant disability.
- Causes a congenital anomaly or birth defect.
- Results in a significant medical incident (considered to be a serious study related event because, based upon appropriate medical judgment, it may jeopardize the subject and may require medical or surgical intervention to prevent one of the outcomes listed in this definition).

6.6 Unanticipated problem (UP) definition:

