6.8 Data and Safety Monitoring Plan

Data and safety monitoring will involve AE reporting by site study staff, and review of AE, SAE, UP, protocol deviations (PD), dropouts, complaints, or breaches of confidentiality by the DCC. Subjects will be encouraged to report any study-related and/or health problems at any time to the study site staff. AEs reported to the DCC and other data and safety issues found during site visit audits will be subject to additional reporting (IRB, FDA) per reporting policies.

A Data Safety Monitoring Board (DSMB) will be assembled for subject safety. This board will consist of members who have expertise in any of the following: neurology, multiple sclerosis, clinical trials, and medical safety. The board members will document their lack of conflict of interest and approve a DSMB Charter prior to study start. All members of the DSMB will review and approve study protocol and informed consent forms for all study sites prior to enrollment.

The DSMB Chair or DSMB member designee reviews SAE in real time according to reporting timetables (6.0). The DSMB receives quarterly reports, developed by the DCC and SCC, which includes aggregate reports of AE, SAE, UP, and PD, including the safety lab data according to Limited Reporting of AE (6.3) presented grouped by study arm and study site (as necessary). The board will meet every six months, as necessary, to review quarterly reports, enrollment/screening progress, data collection problems, and missing data. No non-safety related study outcome analyses will be performed until study completion, unless the committee determines there is a compelling reason to do so related to patient safety concerns. The DSMB also meets when the last subject completes participation. The DSMB will provide a written summary of each meeting to the PI with a statement about appropriateness of continuation of the study. DSMB reports are communicated at least annually to the Central IRB and non-VA IRBs.

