8.2 Ongoing communication

Local site investigators will participate in regular LSI Research Teleconferences led by [name] and the PM to discuss study-related matters including but not limited to IRB issues, training, study preparation, subject recruitment, data collection, REDCap database entry, adverse events, budgets, and publications. The PM with conduct regular (e.g. monthly) teleconferences with site study staff for data collection and related issues. LSIs are expected to hold regular meetings with their site research staff in order to review study progress, review adverse events, and other study matters. Email will also be utilized as a primary method of communicating information about changes to the protocol, informed consent, and HIPAA authorization. Communication about AEs, SAEs, unanticipated problems, or DSMB reports will also be conducted by email, phone, or the LSI teleconferences as appropriate to the level of urgency of information transmitted. This information will be relayed to the appropriate IRBs under the direction of the DCC according to the DSMP (sec. 6.8).

Initial and ongoing IRB approval documents will be provided by each study site to the PI to ensure that no study activities occur without IRB approval. Acknowledgment of these notifications will be maintained as documentation of understanding from each study site.

Study sites will be notified when enrolment targets are reached, when sites have completed their final study visits, and when the entire study has completed. Acknowledgment of these notifications will be maintained as documentation of understanding from each study site. Study LSIs will have the opportunity to participate in manuscript preparation with authorship order related to recruitment achieved and/or level of participation in manuscript editing.

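### Table 6.3a keeps possibly related unanticipated problems out of routine central reporting, in conflict with Sections 4.0, 6.0, 6.8 and 8.2

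*Combined protocol and SAP*

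**What the plan says.** Section 6.3 limits what sites send to the DCC: "Not all AE captured at sites are reported to the DCC". Table 6.3a gives the routing by intensity and relatedness. Its row "UP with risk to subjects or others" reads REDCap for related, REDCap for probably related, and site AE log only for both possibly related and unrelated. The text above the table adds: "Serious AE (SAE) and select UP and PD are reported under expedited guidelines according to IRB and other monitoring entity requirements".

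Other sections describe UP reporting without reference to relatedness:

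- Section 6.0, opening sentence: "All SAE, UAP, and PD are reported to the IRB within defined timelines". UAP is read here as the same thing as UP.
- Section 4.0, on the DCC: "The DCC will receive reports from all study sites regarding adverse events (AE), serious adverse events (SAE), unexpected problems (UP), and protocol deviations (PD"), and it is to "ensure proper reporting to IRBs per reporting requirements".
- Section 6.8 lists UPs among the items the DCC reviews. It has the DCC and the Statistical Coordinating Center (SCC) build quarterly DSMB reports that include aggregate UPs.
- Section 8.2, directly after a sentence that names unanticipated problems: "This information will be relayed to the appropriate IRBs under the direction of the DCC according to the DSMP (sec. 6.8").

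Section 6.6 defines a UP broadly. It covers events that raise risk above what was previously known, and no one need have been harmed.

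**The concern.** A site holding a possibly related UP has two instructions that do not fit together. Under the table it stays on the local log. Under Sections 4.0 and 8.2 the DCC receives UPs and directs their relay to IRBs, and Section 6.0 says all of them get there. The DCC cannot review or direct the reporting of an event that its own table tells sites not to send.

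What is at stake is the pooling of early, uncertain events across sites. The protocol supplies an example in Section 2.0 (Preliminary Studies). In the pilot, no unexpected harmful events were attributed to lipoic acid at the time. A later review, made in light of safety data from the present trial, re-attributed a biopsy-proven glomerulonephritis and a second case of proteinuria to the drug. First attributions were revised once more evidence was available. The renal findings now have an always-report footnote under Table 6.3a. A problem of a kind not yet recognised would not.

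**Working it through.** The core of this is a comparison of rules, so the passages are set side by side. The documents state no figure to reproduce.

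**Step 1. Where Table 6.3a sends each kind of event.**

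| Event | Related | Probably | Possibly | Unrelated |
|---|---|---|---|---|
| Mild AE | REDCap | log | log | log |
| Moderate AE | REDCap | REDCap | log | log |
| Severe AE | REDCap | REDCap | REDCap | REDCap |
| SAE | REDCap | REDCap | REDCap | REDCap |
| UP with risk | REDCap | REDCap | log | log |

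The footnote sends three laboratory findings to REDCap whatever their intensity or relatedness: a rise in ALT or AST grade, new ACR above 300 mg/g, and new eGFR below 60.

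The UP row is identical to the moderate AE row, so classing a moderate event as a UP adds no reporting to the DCC. Moderate protocol deviations go to REDCap, although Section 6.7b lets that grade cover harm or risk that is not significant.

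**Step 2. What is left uncovered.** Take all possibly related UPs with risk. Remove those that are also severe AEs, SAEs or listed laboratory changes, since other rows or the footnote catch them. What remains is UPs that are mild or moderate, or that caused no harm. Section 6.6 expressly allows the last kind.

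**Step 3. Which statements the table conflicts with.**

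- *Sections 4.0 and 6.8* have the DCC receive and review UPs. The conflict is direct, because the table governs exactly that transfer.
- *Section 6.0* requires all UPs to reach the IRB but names no route. The conflict arises when it is read with 4.0 and 8.2, which put the DCC in the route.
- *The word 'select' in Section 6.3* qualifies expedited reporting. It does not narrow the word 'All' in 6.0.

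**Step 4. The DSMB.** Section 6.8 has the DCC and SCC build the UP aggregates. An event not sent to the DCC would therefore be missing from them. This is an inference. The phrase "including the safety lab data according to Limited Reporting of AE (6.3") follows the mention of laboratory data and may qualify only those data, so it is not relied on here.

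**Step 5. A parallel mismatch.** Section 6.7 says every protocol deviation is entered into REDCap, then says mild ones are kept on the site log only, as the table does. Section 6.0 again says all go to the IRB.

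**Step 6. Scale, for illustration only.** Inputs from the Synopsis and Section 5.1a: 118 subjects, 59 per arm, 11 listed sites. The rate of a new problem is an assumption, because the documents give none.

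- Subjects per site: 118 / 11 = 10.7.
- Expected cases in the lipoic acid arm = 59 × rate. At 1%: 0.6. At 3%: 1.8. At 4%: 2.4. At 10%: 5.9.
- Lipoic acid subjects per site, if sites were equal in size: 59 / 11 = 5.36. Chance that two cases fall at different sites: 1 − (5.36 − 1) / (59 − 1) = 1 − 0.075 = 0.92.

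On those assumptions, a problem affecting 3–4% would give about two cases, usually at two different sites.

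**The case against.** A reader might infer that the DCC and the DSMB would never learn of these events, or that the protocol has a single rule sending every UP to the IRB through the DCC. The documents support neither.

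- **Other ways to surface.** Section 6.1 refers uncertain attributions to the medical monitor, who under Section 4.0 is a DSMB member. Severe AEs, SAEs and the listed liver and kidney changes reach REDCap regardless, which covers much of the known risk. Section 8.2 provides for UPs to be discussed by email, phone or teleconference. Yearly monitoring (8.3) and site audits (6.8) may find log entries.
- **The DCC is not the only route to an IRB.** Section 6.1 has the DCC assist the Clinical Coordinating Center with IRB reporting. Section 8.1 makes the principal site responsible for ongoing reporting to the VA Central IRB. Section 5.1m has findings that could affect subjects' health or welfare reported to the appropriate authorities. Keeping a UP out of REDCap does not by itself keep it from an IRB.
- **The limit may be deliberate.** The title of 6.3a names UPs among the items with limited reporting. Section 4.0 is a general description of roles, tied to reporting requirements, and its sentence also covers AEs, which 6.3 plainly limits.

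The first two arguments stand and set the size of the point. The third stands in part. If the limit is intended, Sections 4.0, 6.0, 6.8 and 8.2 still need to say so. The other ways to surface are also weaker than routine reporting: referral depends on someone regarding the attribution as uncertain, and verification of AE reporting is only something a yearly visit may include.

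**Conclusion.** The point holds in a limited form. Table 6.3a and the sections on UP reporting do not agree and must be reconciled. Followed as written, the table leaves possibly related UPs that are mild, moderate or harmless out of routine DCC data unless they are among the listed laboratory changes. By inference it also leaves them out of the quarterly DSMB aggregates. UPs judged unrelated are routed the same way, and the same conflict applies to them.

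The number of events affected cannot be derived from the documents. The figure of about two cases rests on an assumed rate of 3–4%, and the spread across sites on an assumption of equal site sizes. The conclusion needs neither, since it follows from the routing rules. It does rest on reading UAP as UP, and on the DSMB aggregates being built from what the DCC holds. The bold type that marks expedited items in Table 6.3a cannot be read in the text available, so nothing is concluded about expedited timelines.

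**What to change.** 1. In Table 6.3a, change the possibly related cell of the UP row from site log to REDCap, on the timeline that the row already sets for related and probably related UPs.
2. That cell alone does not remove the conflict with the word 'All' in Section 6.0. State one rule, worded the same in 6.0, 6.3a and 6.7, for where UPs judged unrelated and mild protocol deviations are reported. If some are to stay on the site log, 6.0 and the first statement in 6.7 should say so.
3. Align the DCC's role in 4.0, 6.8 and 8.2 with that rule, and say in 6.8 whether the DSMB's UP aggregates include all UPs or only those in REDCap.

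The cost is one table cell, matching wording in a few sections, and a few extra REDCap entries. No outcome, analysis or sample size changes.

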Central MRI Reading Site: The Central MRI Reading Site will receive MRI images from all study sites, perform QC monitoring of images and facilities, provide feedback on image quality issues, conduct all study related image analyses, and enter the analysis results into the study database. The Central MRI Reading Site will have access to PHI from all study subjects.

Data Safety and Monitoring Board (DSMB): The DSMB will develop the DSMB charter and will meet at least yearly to review aggregate safety data and study progress. The DSMB will provide a report to the PI with recommendations regarding ongoing conduct of the study. As a member of the DSMB, [name] will be the Medical Monitor for this study. [name], a nephrologist at OHSU, will monitor any abnormal kidney function at the time of entry of during the course of treatment. The DSMB will have access to PHI from all study subjects.

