a. Proteinuria monitoring: Subjects must have urine protein *monitored every 3 months* for the duration of the study. Subjects must pause study drug if they skip or miss a visit until draw can occur.

Subjects with baseline (screening) negative or trace proteinuria may participate in the study. Subjects with baseline 1+ or higher proteinuria are further tested for albumin to creatinine ratio (ACR): 1) ACR \leq 300mg/g may participate, 2) ACR >300mg/g are excluded and receive referral to PCP. No repeat screening for proteinuria in subjects who have ACR >300mg/g will be done.

Subjects who experience 1+ or higher proteinuria during the study are further tested for ACR: 1) ACR \leq 300mg/g may continue participation, 2) ACR >300mg/g permanently stop study drug and receive referral to PCP or nephrologist along with notification of the Medical Monitor. A referral to Nephrology is recommended if ACR>1000mg/g. A kidney biopsy is recommended if proteinuria >300 does not resolve within 6 weeks of drug cessation.

b. Renal function monitoring: Subjects with baseline eGFR ≥ 60 may participate in the study. Subjects with baseline eGFR<50 are excluded. Subjects with baseline eGFR 50-59.9 are retested: 1) eGFR ≥ 60 may participate in the study, 2) eGFR<60 are excluded.

Subjects who experience eGFR 50-59.9 during the study are retested within 1 month: 1) eGFR \geq 60 may continue participation in the study, 2) eGFR<60 permanently stop study drug and are referred to PCP. Subjects who experience eGFR<50 during the study permanently stop study drug and referred to PCP. Regardless of the eGFR, if the eGFR decreases by 25% or more compared to the baseline eGFR, the Medical Monitor should be notified and should review the information to determine the next course of action.

c. Liver function monitoring: Abnormal liver laboratory results are graded according to the Common Terminology Criteria for Adverse Events v5.0 (https://ctep.cancer.gov/protocoldevelopment/electronic_applications/ctc.htm).

Subjects who have stable and asymptomatic baseline Grade 1 abnormal laboratory liver values may, at the discretion of the site treating neurologists, participate in the study. Subjects who experience laboratory abnormalities of Grade 1 during the study will be permitted to continue at the full dose of study drug unless advised otherwise by the DSMB or other monitoring entities.

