Abnormal laboratory tests may be repeated immediately if laboratory testing error is suspected. Laboratory tests should be repeated within 1 month for any liver values reaching a Grade 2 or greater.

If laboratory liver value(s) are still Grade 2 or greater by 1 month, the investigational drug will be reduced by 50% and levels checked again within 1 month. The rationale is that liver-related abnormalities are often dose-dependent. If laboratory liver value(s) improve to Grade 1 or less, the study drug dose is then increased to the full dose. If the same subsequent laboratory value(s) worsen again at the full dose, the subject may continue for the study duration at the 50% dose as long as subsequent laboratory values do not meet Grade 2 or greater levels. If subjects on a 50% dose demonstrate continued Grade 2 value(s) at a maximum of 1 month, subjects should stop the investigational drug. Those subjects for whom laboratory values do not improve to Grade 1 or better levels after 2 months off study drug permanently stop study drug. Only two investigational drug cessations are allowed for each subject. Any subject who experiences a third Grade 2 or higher laboratory test must permanently discontinue the investigational drug. If in question, permanent study drug discontinuations can be discussed with the Medical Monitor to establish the relationship of the laboratory result to the investigational drug. Subjects continue study procedures following the study flowsheet until study end during any investigational drug dose reductions and temporary cessations (see 5.1d for special handling of MS clinical relapse evaluations).

Safety laboratory results will be reviewed by site treating neurologists within 3 business days to determine if dose adjustments or safety reporting is required along with documentation and reporting as required (section 6.0 Reporting).

Sexually active female subjects capable of becoming pregnant and female partners of sexually active male subjects will be asked to use effective birth control during the study. If a female participant or partner of a male participant becomes pregnant during the research study, study personnel must be notified immediately. Subjects will be advised not to breastfeed while taking this investigational drug. Screening for pregnancy in female subjects of child-bearing potential will be conducted via pregnancy tests at study visits.

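### An eGFR fall of 25% or more triggers action in 5.1m but is missing from the always-report list in 6.3a, so with a baseline of 80 or more it need not reach the DSMB by arm

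*Combined protocol and SAP*

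**What the plan says.** Section 5.1m b sets two kinds of on-study eGFR trigger.

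- **Relative:** at any eGFR level, "if the eGFR decreases by 25% or more compared to the baseline eGFR, the Medical Monitor should be notified", and that person then decides what follows.
- **Absolute:** a value of 50-59.9 is retested within a month, and if not recovered, "2) eGFR<60 permanently stop study drug and are referred to PCP". For lower values, "Subjects who experience eGFR<50 during the study permanently stop study drug and referred to PCP".

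The proteinuria rule in 5.1m a is worded differently. Subjects stopped for ACR above 300 mg/g "receive referral to PCP or nephrologist along with notification of the Medical Monitor".

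Section 6.3 states that only some site-recorded events go to the Data Coordinating Center. A grid of intensity by relatedness decides which, and a footnote overrides the grid for a short laboratory list: "Increases after Screen in CTCAEv5 grades (ALT, AST), new ACR >300mg/g, and new eGFR<60 are always reported in REDCap". Section 6.8 gives the DSMB quarterly aggregate reports, "including the safety lab data according to Limited Reporting of AE (6.3) presented grouped by study arm".

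Section 4.0, in its DSMB paragraph, makes one board member the Medical Monitor and says that a nephrologist "will monitor any abnormal kidney function at the time of entry of during the course of treatment". For the liver, 5.1m c acts on a wide class: "Laboratory tests should be repeated within 1 month for any liver values reaching a Grade 2 or greater".

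**The concern.** The list of findings that call for action and the list that is always reported centrally differ on eGFR. A relative fall that the plan considers serious enough for individual medical review has no guaranteed place in the only routine report that compares the arms.

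If the fall is not on the list, whether it reaches the database depends on how the site grades and attributes it. Attribution is a weak filter here. The Preliminary Studies text in section 2.0 records that a pilot case of glomerulonephritis and one of proteinuria were attributed to lipoic acid only on later review. Counts by arm do not depend on attribution, which is why a monitoring board wants them. Notices to the Medical Monitor one at a time do not give a comparison between arms.

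There is also a smaller inconsistency within 5.1m. A renal stop based on ACR obliges the site to tell the Medical Monitor. A renal stop based on eGFR does not, unless the fall also reaches 25%.

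**Working it through.** The plan gives no figure to reproduce here, so the check compares thresholds.

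**Inputs.** Let B be baseline eGFR and v an on-study value. I take B as the qualifying screening value, because the 5.5a flowsheet limits baseline-visit laboratory work to a pregnancy test.

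- Entry (5.1m b): B of 60 or more.
- Always reported (6.3a footnote): v < 60.
- Medical Monitor notified (5.1m b): v ≤ 0.75 × B.
- Permanent stop (5.1m b): v < 50, or v of 50-59.9 and still below 60 on retest.

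**Step 1. Medical Monitor trigger met, but not on the always-report list.** This needs 60 ≤ v ≤ 0.75 × B, which is possible only if B ≥ 60/0.75 = 80. The largest unlisted fall is 1 − 60/B.

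| Baseline B | 0.75 × B | Unlisted values of v | Largest unlisted fall |
|---|---|---|---|
| 80 | 60.0 | 60 | 25.0% |
| 90 | 67.5 | 60 to 67.5 | 33.3% |
| 100 | 75.0 | 60 to 75 | 40.0% |
| 120 | 90.0 | 60 to 90 | 50.0% |

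Example: 100 to 65 is a fall of 35/100 = 35%. The Medical Monitor is notified and the footnote does not apply. For B below 80, a 25% fall is already below 60 and is listed, so this gap does not exist.

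**Step 2. What the grid does with an unlisted fall.** In 6.3a, mild events reach REDCap only if judged related, and moderate events only if judged related or probably related. Severe and serious events always do. Of the eight mild and moderate cells, five (mild: probably, possibly, unrelated; moderate: possibly, unrelated) stay on the site log. A fall from 100 to 65 graded moderate and possibly related would therefore not be sent.

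**Step 3. Permanent eGFR stop without the Medical Monitor trigger.** This needs v < 60 and v > 0.75 × B, so B < 80. For the immediate stop below 50 it needs B < 50/0.75 = 66.7.

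- 75 to a confirmed 58: 17/75 = 22.7%. Stop, no required notice.
- 62 to 49: 13/62 = 21.0%. Immediate stop, no required notice.

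For B of 80 or more, any value below 60 is a fall of more than 25%, so notice is required.

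**Step 4. The two gaps together.** They affect complementary baseline ranges: 80 or more for the first, 60 to below 80 for the second. Every eGFR stop rests on a value below 60, which the footnote always reports, so the value behind each stop does reach the DSMB by arm.

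**Step 5. Liver.** Section 5.1m c acts on any liver value at Grade 2 or above, while the footnote names ALT and AST. The available text does not itemise the liver panel, and ALP and GGT appear only in the list of abbreviations. Whether there is a mismatch depends on what the panel contains.

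**The case against.** The plan has several answers, and some of them stand.

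- **A 25% fall does reach the board in one sense.** The Medical Monitor must be told, must review it, and is a DSMB member. That stands, but it is one case at a time and not a comparison by arm.
- **The footnote is not the only route.** The grid sends all severe events and some milder ones to REDCap. Section 5.6b lets the DSMB ask for analyses at any time, 6.8 holds back only outcomes unrelated to safety, and the DSMB charter, which could add tables, is not among the documents. A reader might infer that the board sees renal data by arm solely once an absolute threshold is crossed; these routes show otherwise. What is missing is a guaranteed, routine entry. The by-group comparison of laboratory changes in 5.6b otherwise comes at study completion.
- **eGFR stops are not hidden.** A reader might infer that some permanent stops escape the people who review kidney function. The documents do not support that: the value below 60 is always reported, the Medical Monitor sits on the board, and section 4.0 gives a nephrologist oversight of any abnormal kidney function. What is absent is a stated route and a required prompt notice.
- **The proteinuria signal is covered.** Urine protein is tested every three months, and a new ACR above 300 mg/g is always reported and notified. It is also tempting to argue that a relative eGFR fall would have exposed the pilot cases sooner. Nothing in the documents says so; those cases were glomerulonephritis and proteinuria.
- **Limited reporting is a deliberate choice.** A case-review trigger and an aggregate list serve different purposes, and no passage flatly contradicts another. This is fair, and it makes the point an improvement to safety reporting rather than the correction of an error.

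**Conclusion.** The point holds in a limited form. For subjects with baseline eGFR of 80 or more, a fall of 25% or more that stays at or above 60 triggers individual review but has no assured place in the DSMB's by-arm laboratory data. Such a fall can be as large as 40% from a baseline of 100. For subjects with baseline 60 to below 80, a permanent eGFR stop can occur without required prompt notice to the Medical Monitor, unlike an ACR stop, although the value itself is reported by arm. The liver item is conditional on the panel.

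This assumes that baseline is the qualifying screening value and that the quarterly reports contain what 6.3 sends and no more. The documents give no distribution of baseline eGFR and no expected event rate, so the number of subjects affected cannot be estimated. With names removed, it also cannot be seen whether the nephrologist and the Medical Monitor are separate people. The change is worth making because it is cheap and concerns an organ risk that the plan itself recognises.

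**What to change.** 1. In the 6.3a footnote, add an eGFR decrease of 25% or more from baseline to the findings always entered in REDCap, and count it by arm in the quarterly DSMB report. State which value is the baseline.
2. Reconcile section 4.0 with 5.1m a and b, so that the protocol states how eGFR-based stops reach the Medical Monitor and the study nephrologist, consistently with the ACR rule.
3. Itemise the liver panel. If any test other than ALT or AST drives action under 5.1m c, align the liver item in 6.3a with it.

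These changes concern reporting and notification alone; no stopping or dosing threshold is touched. Renal function is already measured at screening and at M3, M6, M12, M18 and M24 (5.5e), and 5.6b already calls for changes from baseline, so no new test is needed. The cost is a few sentences, a REDCap flag, one pass over values already collected, and slightly more entries and notifications.
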